## **STATISTICAL METHODS AND CONSIDERATIONS**

We will analyze data from all participants who undergo randomization.

### **Analysis of Primary Endpoint**

We will compare within-person changes in daytime total sleep time (primary: diary, secondary: actigraphy) averaged over a two-week baseline and treatment period between groups (Lemborexant vs. placebo) using linear mixed effects models (repeated measures of outcomes, with time, treatment group, and time by group interactions as predictors, as well as potentially random intercepts, and random slopes to accommodate between subject differences in rates of change). We will calculate 95% confidence intervals for the time by group interaction to provide a range of differences in change that are consistent with the data and test interactions using likelihood ratio tests. Linear mixed models will also be carried out to test the other proposed study outcomes. This will accommodate an intent to treat analysis. Covariates, such as number of sleep entries (i.e., number of available diary/actigraphy daytime sleep attempts), will be included in analyses if needed.

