## PROTOCOL SYNOPSIS

TITLE	Effects of Lemborexant vs placebo on total daytime sleep in shift workers: A randomized controlled trial
SPONSOR	Eisai Co, Ltd
FUNDING ORGANIZATION	Eisai Co, Ltd
NUMBER OF SITES	1
RATIONALE	Insomnia and daytime sleepiness are common among shift workers, and there is a lack of available treatments. Lemborexant, which is a hypocretin/orexin antagonist, is a plausible treatment to improve sleep in shift workers
STUDY DESIGN	This is a randomized, double-blind, placebo-controlled phase 4 study.
PRIMARY OBJECTIVE	Test the effect of Lemborexant on daytime total sleep time (measured via sleep diary) compared to placebo
NUMBER OF SUBJECTS	45 night shift workers enrolled; accounting for attrition, we expect 30 completers
SUBJECT SELECTION CRITERIA	
Inclusion Criteria:
 
 
• 20 to 60 years old;
 
• Full-time night shift work (at least 6 hours per shift, 4 days per week or 32 hours per week);
 
• Employed as a night shift worker for at least 3 months;
 
• Self-reported difficulty sleeping during the daytime (Insomnia Severity Index>8).
 
 
Exclusion Criteria:
 
 
• Pregnancy (verified by urine pregnancy test) or plan to become pregnant in the next 3 months;
 
• Currently breastfeeding;
 
• Inadequate opportunity for sleep during the daytime (< 7 hours opportunity) after overnight shift.
 
• Extreme circadian preference (based on Horne & Ostberg Morningness-Eveningness Questionnaire);
 
• Severe depressive symptoms (>25 on CES-D);
 
• Unwillingness to discontinue sleep aids (prescription or non-prescription) during the study period;
 
• Presence of sleep disordered breathing (verified by Z-machine);
 
• Self-reported diagnosis of narcolepsy, restless legs syndrome;
 

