	
 
Intake of >600mg of caffeine per night shift or use of stimulants during night shift, rotational, or irregular shifts;
 
Unstable or untreated medical or psychiatric condition based on clinical interview.
 
Severe hepatic or renal impairment (based on chemistry panel);
 
Self-reported use of digoxin or strong or moderate cytochrome P450 3A4 isozyme inhibitors or cytochrome P450 3A4 isozyme inducers for 6 months prior to or during the study
 

TEST PRODUCT, DOSE, AND ROUTE OF ADMINISTRATION	
Product Lemborexant at 5mg dose (titration up to 10mg based on participants perceived benefit)
 
Lemborexant will be administered immediately prior to daytime sleep attempt over the course of 3 weeks. The first week will constitute the titration week. Two-week treatment phase begins following titration week.

CONTROL PRODUCT, DOSE AND ROUTE OF ADMINISTRATION	
Placebo
 
Placebo will be administered immediately prior to daytime sleep attempt over the course of 3 weeks. The first week will constitute the titration week. Two-week treatment phase begins following titration week.

DURATION OF SUBJECT PARTICIPATION AND DURATION OF STUDY	
Subjects will be on study for up to 6 weeks
 
Screening: 1 day
 
Medication tapering (if needed): up to 1 week
 
Baseline sleep assessment: 2 weeks
 
Titration phase: 1 week
 
Treatment phase: 2 weeks
 
The total duration of the study is expected to be 12-months.

EFFICACY EVALUATIONS	
PRIMARY ENDPOINT	
 
Primary Outcome: Daytime total sleep time (sleep diary) averaged over 2-week treatment period. Participants will be asked to take their medication immediately prior to their daytime sleep attempt
 

SECONDARY ENDPOINTS	
 
Daytime total sleep time (actigraphy) averaged over 2-week treatment period
 

OTHER EVALUATIONS	
SAFETY EVALUATIONS	Adverse event assessment, by history, at post-intervention follow-up.
PLANNED INTERIM ANALYSES	None

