## Criteria for evaluation

### Primary Efficacy Endpoint

- Daytime total sleep time (sleep diary) averaged over 2-week treatment period. Participants will be asked to take their medication immediately prior to their daytime sleep attempt

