### Dosage/Dosage Regimen

*Following the baseline assessment, participants will be randomized to either drug or placebo. Those in the drug condition will be provided 5mg Lemborexant and re-evaluated one week later as part of the titration period. Those who wish to increase their dose to 10mg may do so for the 2-week drug period. The same option will be provided to the placebo condition.*

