## APPENDIX 1.

Screening	

• Computer assessed eligibility

Visit #1	

• Eligibility confirmed

• Medical history interview

• Medication assessment

• Psychiatric clinical interview

• Sleep disorder clinical interview (SCISD)

• Informed consent

• Blood chemistry

• Questionnaires

Medication tapering (if needed)	

• Tapering protocol (supervised by [name]; washout period prior of at least 5 half-lives of any drug with a significant effect on sleep/wake function)

Baseline Sleep Assessment (2-weeks)	

• Wrist actigraphy

• Sleep diary

• OSA evaluation (Z-machine, 1-night)

Visit #2	

• Eligibility confirmed

• Medication assessment

• Adverse Event form

• Pregnancy test

• Randomization (5mg Lemborexant/placebo)

- 15 participants (Lemborexant, 5mg)

- 15 participants (placebo)

• Drug/Placebo distribution (MemsCaps)

• Patient global impression

• Clinician global impression

Titration (1-week)	

• Wrist actigraphy

• Sleep diary

---

Visit #3	

• Adverse event form

• Medication assessment

• Patient global impression

• Clinician global impression

• Drug/Placebo distribution (MemsCaps)

Treatment (2-weeks)	

• Wrist actigraphy

• Sleep diary

Visit #4	

• Adverse event assessment

• Medication assessment

• Patient global impression

• Clinician global impression

• Questionnaires

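### Titration-week diaries are collected after randomisation but left out of the primary model, which could bias the estimate in either direction if people lost after that week differ between arms

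*Combined protocol and SAP*

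**What the plan says.** - **Order of events.** Dosage/Dosage Regimen: "Following the baseline assessment, participants will be randomized to either drug or placebo". Randomisation is at Visit 2, the titration week runs from Visit 2 to Visit 3, and the Synopsis adds "Two-week treatment phase begins following titration week".
- **Data collected.** In Appendix 1 the row beginning "Titration (1-week" lists wrist actigraphy and sleep diary. Evaluations by Visit lists them only for the baseline and treatment assessments, so the titration-week diary rests on Appendix 1 alone.
- **Endpoint.** "Daytime total sleep time (sleep diary) averaged over 2-week treatment period".
- **Model.** Analysis of Primary Endpoint fits a linear mixed model to values "averaged over a two-week baseline and treatment period between groups", with time, group and their interaction. The titration week is not named.
- **Analysis set and missing data.** "We will analyze data from all participants who undergo randomization". The only sentence bearing on missing values is "This will accommodate an intent to treat analysis"; no missing-data assumption or sensitivity analysis is given.
- **Attrition.** The Synopsis says "accounting for attrition, we expect 30 completers" from 45 enrolled. Sample Size and Randomization applies its 30% attrition between recruiting 45 and randomising 30. Method of Assigning Subjects allows up to 45 to be randomised.

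**The concern.** The titration week supplies the first outcome data after randomisation. It ends at Visit 3, where perceived benefit is reviewed, so a person's early response is a plausible reason to leave at that point. A likelihood-based mixed model handles missing values properly only when the missingness is explained by data in the model. With two periods, the only observed outcome for someone who leaves after titration is the baseline average. The model cannot use the week that may explain the departure, although the trial has recorded it.

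Two things are at stake. All randomised participants are analysed in name, but those without a treatment-fortnight diary contribute little. And if the people lost differ between arms in their titration-week sleep, the group difference in change is estimated from groups that are no longer comparable.

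**Working it through.** **The plan's own figure.** With d = 1.39, two-sided alpha 0.05 (assumed; consistent with the 95% interval) and 90% power, the noncentral t calculation gives 12 per arm (power 0.902), as stated. Power is 0.957 at 15 per arm and 0.836 at 10. For attrition, 30/(1 - 0.30) = 43, against 45 stated. The sample size reproduces and this point does not change it.

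**What leavers add now.** In a simulation with 15 per arm, SD 1, baseline correlation 0.5 and 22% lost equally in both arms, the standard error was 0.382 for the planned model, 0.388 for completers only and 0.360 with no loss. The planned model is close to a completer analysis.

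**Size of the possible bias.** None of these inputs is in the documents: SD 60 min; effect 60 min, with 80% (48 min) present in titration; correlation 0.5 of baseline with each later period; 0.8 between titration and treatment; those with titration sleep below a cut-off leave.

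If a fraction p of an arm leaves, let z be the p-quantile of the standard normal and λ = φ(z)/(1 - p).
- The retained titration mean is too high by s = 60λ, the retained treatment mean by 0.8s and the retained baseline mean by 0.5s.
- The two-period model corrects only through baseline, with pooled within-arm slope b among those retained. It leaves an error of s(0.8 - 0.5b) in that arm.

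Worked case, 30% of placebo only:
- z = -0.524, φ = 0.348, λ = 0.348/0.70 = 0.497, s = 29.8 min.
- The retained titration variance ratio is 1 + zλ - λ² = 1 - 0.260 - 0.247 = 0.493.
- Among retained placebo, baseline variance is 1 - 0.25 × 0.507 = 0.873 and covariance with treatment is 0.5 - 0.4 × 0.507 = 0.297.
- Pooling with the intact arm, b = (0.7 × 0.297 + 0.5)/(0.7 × 0.873 + 1) = 0.44.
- Error = 29.8 × (0.8 - 0.22) = 17.3 min. The placebo mean is too high, so the effect is biased by about -17 min.

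The same steps give:

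| Who leaves | Lost, placebo / active | Lost of all randomised | Bias, two-period model |
|---|---|---|---|
| Placebo only | 7% / 0 | 3.5% | -4.9 min |
| Placebo only | 30% / 0 | 15% | -17.3 min |
| Active only | 0 / 7% | 3.5% | +4.9 min |
| Active only | 0 / 30% | 15% | +17.3 min |
| One cut-off for both arms | 7% / 1.1% | 4.1% | -3.9 min |
| One cut-off for both arms | 30% / 9.3% | 19.6% | -11.4 min |
| Equal fraction in each arm | any | any | 0 |

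With one cut-off, the active arm's cut-off lies 48/60 = 0.8 SD lower relative to its mean, so an effective drug alone makes loss unequal. Simulation of the 30% cases gave -17, +17 and -12 min. For scale, the standard error with no loss is √(2 × 3600/15) = 21.9 min, because the change score has variance 2 × 3600 × (1 - 0.5) = 3600.

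**With titration as a third level.** Leaving now depends on a value in the model, and the bias fell to about 0 in each of these cases.

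**Other assumptions.** A second simulation used weaker correlations (0.5 or 0.7 with baseline, 0.1 higher between titration and treatment), an effect of 1 SD and up to 32% lost in an arm. Two-period bias was -0.06 to -0.14 SD with one cut-off, -0.08 to -0.20 SD for placebo-only loss and +0.07 to +0.19 SD for active-only loss. Equal loss gave -0.008 to -0.005 SD. All were about 0 with the third level.

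**The case against.** A reader might infer that selective dropout does bias this trial's result, or that 30% of randomised people will be lost after titration. The documents support neither. Bias needs loss that depends on titration-week sleep and also differs by arm. The 30% in Sample Size and Randomization falls before randomisation, and Appendix 1 randomises 15 and 15. The Synopsis and the method of assignment are loose enough that later loss cannot be excluded, but none of them plans it.

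These further points also stand:
- Early Discontinuation of Study Drug encourages people who stop drug to complete remaining procedures, so stopping need not mean a missing diary. Someone who leaves partway through the fortnight still has entries to average.
- Keeping titration out of the endpoint is legitimate, and the proposal does not put it in.
- Precision does not always improve. At 30% random loss, root mean squared error fell from 25.7 to 23.9 min. With equal selective loss, simulations disagreed (24.4 to 23.5 min in one, 21.9 to 23.7 in another). With the weaker correlations the standard error rose slightly, for example from 0.373 to 0.385 SD at 22% placebo-only loss.
- The repair is partial if leaving depends on unseen treatment-period sleep: bias went only from -0.21 to -0.17 SD with one cut-off and from -0.28 to -0.23 SD for placebo-only loss.
- The dose decision at Visit 3 may make the titration-treatment relation differ by arm, which a covariance pooled across arms misses. Supposing, for illustration, a 40 min gain in poor drug responders after a dose change, about -6 min remained after the fix in the unequal-loss cases.

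These limit the size of the claim. They do not explain leaving a scheduled post-randomisation outcome out of the model.

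**Conclusion.** The point holds as a cheap improvement. The planned model leaves out outcome data that the trial schedules after randomisation, and someone without a treatment-fortnight diary then adds almost nothing to the primary test. The possible bias is conditional and can go either way: on the inputs listed, roughly -4 to -12 min under a common cut-off, and 5 to 17 min in either direction if only one arm loses people. Set against the 21.9 min standard error, the largest is 17.3/21.9, about 0.8 of a standard error, and the smallest about 0.2. These figures rest on an assumed SD, effect, correlations and sharp leaving rules, and would be smaller with weaker titration-treatment correlation or less selective leaving. If nearly all attrition comes before randomisation, the gain is small. It would be wrong to conclude that the result will be biased, or that the three-level model guarantees that missingness is properly handled.

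**What to change.** In Analysis of Primary Endpoint (and the matching Synopsis text), fit time as a three-level factor: baseline fortnight, titration week, treatment fortnight. Include group-by-time terms and an unstructured within-person covariance in place of the optional random intercepts and slopes. State that the primary contrast remains the between-group difference in change from baseline fortnight to treatment fortnight, so the endpoint is unchanged. Use the same model for actigraphy. In Evaluations by Visit, list diary and actigraphy for the titration week so that it agrees with Appendix 1.

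Because the repair is only partial if leaving depends on unseen values, add one sentence giving the missing-data assumption and one sensitivity analysis that departs from it.

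The cost is wording, since Appendix 1 already schedules the data. The statistical price is six covariance parameters instead of three with 30 people, and sometimes a slightly larger standard error.

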## **STUDY TREATMENTS**

### **Method of Assigning Subjects to Treatment Groups**

Up to 45 eligible patients will be randomly assigned to Lemborexant (5mg) or placebo treatment groups in a 1:1 ratio using a pre-generated randomization scheme developed by the study data management provider.

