## Sample Size and Randomization

We will recruit 45 nightshift workers, accounting for 30% attrition, to randomize 30 participants who will first carry out 2 weeks of sleep diaries and wrist actigraphy and then be randomized to 1 week of Lemborexant (5mg) or placebo during which time they will undergo a titration period. After the week, participants will discuss with the researcher whether they would like to increase their dose to 10mg. Participants will then either take Lemborexant (5 mg-10mg) or placebo for 2 weeks within 60 minutes of attempting daytime sleep. Sample size was calculated based on previously published study demonstrating a robust improvement in diary based daytime total sleep time vs placebo ( $d=1.39$ ) in response to treatment with 20 mg Suvorexant. Based on these data, we would require 12 participants in each condition to detect a large effect size with 90% power. However, to be conservative and ensure that we are adequately powered, we will randomize 15 participants per condition.

---

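### The primary interaction is tested by a likelihood ratio test with no small-sample correction; at 30 participants its true size is about 6%, and a t/F test should replace it

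*Combined protocol and SAP*

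**What the plan says.** The primary endpoint is "Daytime total sleep time (sleep diary) averaged over 2-week treatment period" (Primary Efficacy Endpoint). The Analysis of Primary Endpoint section compares within-person change "averaged over a two-week baseline and treatment period between groups", using a mixed model with time, group and their interaction, "as well as potentially random intercepts, and random slopes to accommodate between subject differences in rates of change". It gives a 95% confidence interval for the interaction and will "test interactions using likelihood ratio tests". The synopsis (Primary Analysis Plan) says the same.

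Neither place names a reference distribution, ML or REML, a degrees-of-freedom method, a bootstrap or permutation alternative, an interval method or an alpha level.

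On numbers, Sample Size and Randomization plans 15 per condition after calculating that "we would require 12 participants in each condition to detect a large effect size with 90% power". Method of Assigning Subjects to Treatment Groups says "Up to 45 eligible patients will be randomly assigned".

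**The concern.** The chi-square reference for a likelihood ratio test is a large-sample approximation. It takes no account of the uncertainty in the estimated variance, which matters with about 28 degrees of freedom. A plan that names the test and no reference will in practice get the software default, and that default is too liberal at this sample size.

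The error falls on the only primary test and runs in one direction: p-values come out too small. If the 95% interval is t-based, it could also include zero while the test is declared significant.

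**Working it through.** **Inputs.** 15 per arm, N = 30; d = 1.39; 12 per arm for 90% power (all Sample Size and Randomization). Upper limit N = 45 (Method of Assigning Subjects to Treatment Groups). Two-sided alpha of 0.05 is an assumption taken from the 95% interval.

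**The plan's own figure.** Power of a two-sample t-test on 2n − 2 df, with noncentrality d·√(n/2):
- n = 12: noncentrality 1.39·√6 = 3.405, power 90.2%
- n = 11: power 87.3%

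So 12 per arm is what a two-sided 5% t-test gives (the normal approximation gives 11). The sample size therefore fits a t-test, while the analysis section names a different test. The match also supports the assumed alpha.

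**The likelihood ratio statistic.** With one baseline and one treatment mean per person, the interaction is the group difference in mean change. With both means present for everyone, the ML statistic is

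LR = N·ln(1 + t²/(N − 2)),

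where t is the two-sample t on change. This holds for an unstructured 2x2 covariance, and for a random intercept whose variance estimate is above zero. Five datasets fitted by ML with a random intercept matched it to four decimals, and the REML Wald t equalled the change-score t.

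**True size.** LR > 3.841 is the same as |t| > √[(N − 2)(exp(3.841/N) − 1)]. At N = 30 this is √(28 × 0.1366) = 1.956, against the exact 2.048 on 28 df.

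| N | LR rejects at \|t\| > | exact cut-off | true size | simulated size | a t-test p of 0.050 becomes |
|---|---|---|---|---|---|
| 24 | 1.954 | 2.074 | 6.35% | 6.35% | 0.038 |
| 30 | 1.956 | 2.048 | 6.05% | 6.04% | 0.041 |
| 45 | 1.958 | 2.017 | 5.68% | 5.69% | 0.044 |

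Each simulation used 2,000,000 null trials; the t-test on the same data gave 5.00%, 4.99% and 5.01%. For the last column at N = 30: t = 2.0484 gives LR = 30·ln(1 + 4.196/28) = 4.19, and chi-square(1) gives p = 0.041.

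**Effect on conclusions at N = 30.** Share of trials with |t| between 1.956 and 2.048: 1.1% under no effect, 2.9% at d = 0.5, 3.5% at d = 0.8, 0.8% at d = 1.39. Power at d = 1.39: 96.5% (likelihood ratio) against 95.7% (t-test).

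**Departures from the simple case, all at N = 30.**
- One covariate acting on change: 6.5%.
- Random-intercept fit on period means: 6.0% to 6.1% for within-person correlation 0.3 to 0.7, and about 7% at correlation 0, where the variance estimate often sits at zero.
- Individual sleeps with random intercept and random period effect (5 to 11 sleeps per period, assumed): 5.9%, within 0.6 to 0.7 points.

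**Random slopes.** A correlated random intercept and slope plus residual has four variance parameters; two means per person supply three covariance elements. That model is not identifiable on period means. This is a fitting problem and does not change the error rate above.

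**The case against.** The strongest reply is that this is a refinement: one percentage point, in a single-site trial of 30, using a conventional method. At the plan's own effect size the verdict changes in 0.8% of trials. That is a fair account of the size, and it limits how much weight the point deserves. It is not a reason to leave the test as it is, since correction is free.

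Second, the plan never says chi-square, and a bootstrap or permutation reference for the same statistic would also cure the problem. This stands: the t/F test is the simplest remedy, not the only one. But the plan names no such reference either, and silence leaves the default or a choice made after the data are seen.

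Third, the closed form assumes normality, complete means, no covariates and a positive variance estimate. That is true. The covariate and boundary cases checked raise the size, so they do not rescue the plan.

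Fourth, disagreement between test and interval is only a possibility. A profile-likelihood interval would agree with the likelihood ratio test by construction, but it would carry the same inflation.

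**Conclusion.** The concern holds, at modest size. The nominal 5% primary test has a true size of about 6% at the planned 30 participants, 5.7% if 45 are randomised and 6.35% if 24 are analysed. These figures rest on a two-sided 5% alpha, the usual chi-square(1) reference, one mean per period per person, normality and complete data. Nothing in the documents supplies a small-sample correction. The point does not threaten a clear result at d = 1.39; it matters for a result near the 5% boundary.

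**What to change.** In Analysis of Primary Endpoint and in the synopsis:

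1. State that the unit of analysis is one baseline mean and one treatment-period mean per participant.
2. Fit by REML with an unstructured 2x2 covariance and no random slope.
3. Replace the likelihood ratio test with a t/F test of the time-by-group contrast using Kenward-Roger or Satterthwaite degrees of freedom, at a stated two-sided alpha.
4. Take the 95% interval from the same fit and t reference. A 1.96 multiplier would have an error rate of 6.0% (REML) or 6.9% (ML) at N = 30.

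If individual sleeps are modelled instead, make the random intercept and the random period effect mandatory, with the same degrees-of-freedom method. Omitting the period effect inflates the error rate whenever true change varies between people. The amount depends on inputs the documents do not give: assuming 8 sleeps per period and a within-person SD of 60 min, it is 9.9% at a change SD of 20 min and 32.8% at 60 min.

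The cost is wording only, in standard software, with no extra participants. Power at d = 1.39 with 15 per arm falls by 0.8 points (96.5% to 95.7%) and stays above the 90% target.
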